The Tolerance of Organic Formula Milk and Its Fecal Microbiome Characteristic in Infants

Study Protocol

April 29th, 2021

The Tolerance of Organic Formula Milk and Its Fecal Microbiome Characteristic in Infants

Protocol

Responsible Personnel

Principal Investigator Contact Information

Name: [name]

Title: MD, PhD

Institution: Allergy and Immunology Division, Department of Pediatrics, Faculty of Medicine, Hasanuddin University

Address: [name]

[contact]

Email: [contact]

Other Contact

Name: [name]

Title: MD, PhD

Institution: Graduate School of Medical Sciences, Faculty of Medicine, Hasanuddin University

Address: [name]

[contact]

Email: [contact]

Summary:

An experimental study aims to investigate the tolerance of organic formula milk on infants supplemented with organic formula milk. This study also observes gut microbiota, short chain fatty acids, nutritional status, and atopic manifestation on infants supplemented with organic formula milk. This study will be done on 50 subjects, with an age of 6-7 months old, 38-42 weeks of gestation, had a birth weight ranging from 2700 grams to 4200 grams, not suffering from any major congenital anomaly, not severely stunted at birth, has a normal thyroid function, not suffering any prominent gastrointestinal disease, not having a severe disease at the beginning of study, and has an approval from their parents. Subjects' diet will be added an organic formula for infant for 3 months, and they will be monitored regularly, since this study starts, at each month, and at the end of this study. The subjects' gut microbiomes will be calculated at every session of monitoring by collecting their fecal samples, and brought to laboratory. Anthropological data (weight, height, body mass index), atopic manifestation, IL-6 and IL-10 will also be collected.

Introduction:

An enormous number of microbiotas inhabit the human intestinal tract. The microbiota forms a unique and complex gut ecosystem by interacting with the host, and this affects the health and diseases of the host in various ways, including the modification of the immune system. Butyrate produced by the gut microbiota promotes differentiation of peripherally derived regulatory T cell (pTreg) in colonic lamina propria through epigenetic modification. Besides, it induces B cell Lymphocyte to secrete IgA (sIgA) which will be transferred to intestinal lumen. sIgA plays an important role in antigen binding and clearance. Additionally, gut microbiota can inhibit histone deacetylases (HDACs) as well. All these functions may have the inflammation control not only in the gut but also in other parts of the body. [1].

The microbiota hypothesis states that the disruption of mucosal regulatory immune responses caused by the perturbation of microbiota due to Western lifestyle factors leads to the development of both Th1- and Th2- mediated disease. It is necessary to have a complex

microbiota in order to prevent some diseases such as allergy, diarrhea, autoimmune disorder, etc. The depletion or deletion of bacterial communities, as associated with an elevated serum IgE level, increases the circulating basophil population, thereby exaggerating the Th2 cell responses and allergic inflammation. It has been clarified that gut microbiota plays a critical role in oral tolerance in mouse model. Various studies have revealed that the microbiota plays an important role in pathogenesis of allergic diseases. It remains unclear how the differences in age, region, dietary intake or other environmental factors such as allergen exposure or infection, affect this role [2,3]. Candidate bacterial taxa have been reported it still remain unclear which bacteria (or other microbes), in which numbers and combinations, and when during the gut colonization process may prevent allergic diseases and asthma [4]. Some different microbiota may produce the same metabolome. For example, one of SCFA (short chain fatty acid), pyruvate acid is produced by *Bacteroides* and *Clostridium* as well.

Imbalance of gut microbiota or dysbiosis may start in early life. The increasing in cesarean section, formula feeding and the use of antibiotics during pregnancy or infancy have the significant impacts on microbial homeostasis.

Objectives of Trial:

1. Primary Objective

- a. To know the acceptability of organic formula milk on infants

2. Secondary Objective:

- a. To determine gut microbiota characteristics on infants supplemented with organic formula milk
- b. To determine gut short chain fatty acids on infants supplemented with organic formula milk
- c. Nutritional status including body mass index.
- d. Atopic manifestation

Hypothesis:

H0 : Organic formula milk is not well accepted by infants

H1 : Organic formula milk is well accepted by infants

Trial Design:

Observational study

Study Population:

Number of samples:

50 subjects

Inclusion criteria:

- Healthy infants 6-7 months of age.
- Gestational age 38-42 weeks
- Birth weight >2700 and <4200 gram
- Not suffering from a major congenital anomaly, severely stunted at birth, not having a thyroid problem, not suffered from prominent gastrointestinal diseases, severe diseases at the time of inclusion (severe pneumonia, severe dehydration, etc)
- Parents want to follow the study by signing the informed consent

Exclusion Criteria:

- Subjects are in the severe disease condition at the time of recruitment
- Severe acute malnutrition

- Have conditions that will influence the nutritional status such as moderate to severe dehydration, organomegaly, edema.

Product Description:

Organic formula milk + solid food/breast feeding

Arla Baby&Me Organic Infant Formula 6-12 months, contains:

Skimmed milk, Lactose, Vegetable oils (Palm oil, Rapeseed oil, Soy bean oil, Coconut oil), Galactooligosaccharide (GOS), Concentrated whey protein powder, Fructooligosaccharide (FOS), Arachidonic acid from *M. alpina*, Docosahexaenoic acid from *C. cohnii*, Minerals (Tricalcium disphosphate, Calcium carbonate, Calcium hydroxide, Potassium chloride, Tripotassium citrate, Trisodium citrate, Sodium chloride, Magnesium chloride, Ferrous sulphate, Zinc sulphate, Copper sulphate, Potassium iodide, Manganese sulphate, Sodium selenite), Vitamins (Retinyl acetate, Cholecalciferol, D-alpha tocopherol, Phytomenadione, L-ascorbic acid, Ascorbyl palmitate, Thiamine hydrochloride, Nicotinamide, Calcium-D-pantothenate, Pyridoxine hydrochloride, D-biotin, Folic acid), Emulsifier (Lecithin E322).

**Contains milk and soy ingredients.*

Outcomes:

The tolerance will be the primary outcome measured by clinical examination and questionnaire. We will measure the outcome every month. The secondary outcomes, gut microbiomes which will be obtained through fecal samples collection. Fecal DNA extraction, polymerase chain reaction amplification and library construction for bar-coded 16S rRNA gene amplicon sequencing, using the Illumina MiSeq platform will be examined. The 16SrRNA gene amplicon sequences will be analyzed using QIIME1.9.0 and operational taxonomic units (OTUs). Fecal SCFAs will be measured by LC-MS/MS. Data will then be calculated to see if there is a significant difference before and after organic formula feeding. Additionally, we also will measure nutritional status, including body mass index, atopic manifestation, IL-6, and IL-10. Measurements of weight, length, and head circumference will be monitored at every visits. Anthropometric data will be collected at the beginning of study, first visit (4 weeks after) and at second visit (end of study) to evaluate the subjects growth.

Conduct of Trial:

All the guardians or parents of the subjects who participate in this study will be interviewed in order to record the dietary and sign for inform consent. Parents will be given a journal to record the subject's diet, any sign of colic on subjects, their quality of sleep, and wellbeing. All the subjects will be fed organic formula milk as a part of their dietary for 12 weeks. Before feeding the formula, the nutritional status will be measured and the subject's fecal will be collected for microbiome and short chain fatty acid (SCFA) examination. Every month the parent will be called in order to assess for child's sickness, allergy, body weight, length, head circumference, and to review their journal.

[figure not shown]

Figure 1. Study Procedure

Description of Visits:

A visit follow up will be done before and after the study, the tolerance, nutritional status (including body mass index) and fecal collection for all subjects will be performed. We will also collect the allergy related data. Each fecal examination will follow a strict cold chain procedure, each sample will be collected directly, bottled, and frozen to minimize error. The frozen samples will be transported in insulated bags with frozen ice blocks before being transferred to -80°C for storage.

Statistical Aspects and Considerations:

A statistical analysis will be performed using r program and STATA 13.0. The Normality of data distribution will be tested using the Shapiro-Wilk test. To evaluate potential associations between factors in relation to fecal microbiome or SCFAs, Spearman's rank correlations will be calculated. A p-value <0.05 will be considered significant.

The model will be adjusted for potential confounders. Estimated associations will be described as odds ratios (ORs) with 95% confidence intervals (CIs). The non-parametric Wilcoxon test for paired samples will be used to compare different laboratory parameters at different times of collecting samples. The Mann-Whitney U test for unpaired samples will be applied to compare different categorical parameter between infants before and after treatment. Multivariable linear regressions will be done to find out the association of different parameters change before and after treatment.

Ethical Aspects: The institutional ethics committee of each participating Hasanuddin University Hospital and Wahidin Sudirohusodo Hospital must be approved the study protocol

References:

1. Ohno H: Gut microbial short-chain fatty acids in host defense and immune regulation. Inflamatian and regeneration.2015;35:114-121.
2. Inoue Y, Shimojo N: Microbiome/microbiota and allergies.Semin Immunopathol.2015;37:57-64.

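### Associations are to be reported as odds ratios, but no analysis named in the plan produces an adjusted odds ratio

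*Combined protocol and SAP*

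**What the plan says.** All the analysis text is in the two paragraphs under Statistical Aspects and Considerations. Spearman's method is assigned to relations with the microbiome and SCFAs: "rank correlations will be calculated". The next paragraph opens with a model that has not been introduced: "The model will be adjusted for potential confounders". The effect measure follows at once: "Estimated associations will be described as odds ratios (ORs) with 95% confidence intervals (CIs".

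Three further analyses are then listed:

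- A paired test, assigned to laboratory values over time: "The non-parametric Wilcoxon test for paired samples will be used to compare different laboratory parameters at different times of collecting samples".
- An unpaired test, the only one assigned to categorical data: "The Mann-Whitney U test for unpaired samples will be applied to compare different categorical parameter between infants before and after treatment".
- Last, the only regression that the plan names: "Multivariable linear regressions will be done to find out the association of different parameters change before and after treatment".

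The outcomes are described under Outcomes. For the primary: "The tolerance will be the primary outcome measured by clinical examination and questionnaire". The secondary outcomes are 16S rRNA microbiome data and fecal SCFAs by LC-MS/MS, and then: "Additionally, we also will measure nutritional status, including body mass index, atopic manifestation, IL-6, and IL-10". Study Population gives 50 subjects, and Conduct of Trial has all of them fed the formula, so there is one group measured repeatedly.

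**The concern.** An odds ratio needs a binary (or ordered categorical) outcome and a model on the log-odds scale. The plan promises odds ratios for its associations, yet the only regression it names is linear. The analyst cannot follow the text literally. The choice of measure, model and outcome for the adjusted results would have to be made outside the plan, possibly after the data have been seen.

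A second problem sits beside it. Where the plan does address categorical data before and after feeding, it uses a test for two independent samples. The before and after values come from the same infants, so the within-infant correlation is ignored, and the test gives no effect size with an interval.

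**Working it through.** No figure in the plan can be reproduced here. The protocol gives 50 subjects but no event rate, standard deviation, effect size or power. The check is to set each named method beside what it produces.

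| Method named | Use assigned in the plan | What it yields | Adjusted odds ratio? |
|---|---|---|---|
| Shapiro-Wilk | Distribution check | Test of normality | No |
| Spearman correlation | Factors against microbiome or SCFAs | Rank correlation, unadjusted | No |
| Paired Wilcoxon | Laboratory values over time | Signed-rank statistic and p-value | No |
| Mann-Whitney U | Categorical parameters, before against after | Rank statistic and p-value for independent samples, unadjusted | No |
| Multivariable linear regression | Change before to after | Adjusted mean difference, or slope per unit of a covariate | No |
| The undefined model | Not stated | Not stated | Cannot be determined |

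**Step 1: the linear model.** Write the change for infant i as D_i = Y_i(after) − Y_i(before), and the model as E(D_i) = β0 + β1·x1i + … + βk·xki. Each βj is the difference in mean change per unit of xj, holding the other covariates fixed, in the units of Y. It is not a log odds, so exp(βj) is not an odds ratio.

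**Step 2: is an odds-ratio model given elsewhere?** No logistic, conditional logistic, ordinal or binomial model appears anywhere in the protocol, nor does a GEE. No confounder is listed, and no outcome is defined as binary.

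**Step 3: which outcomes could support an odds ratio?** Abundances, SCFAs, IL-6, IL-10 and BMI are quantitative, and mean differences suit them. Atopic manifestation could be recorded as present or absent at both times, but no analysis is assigned to it. Tolerance has no scale or cut-off. The first assessment also comes before any formula has been given, so tolerance of the product has no defined baseline value.

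**Step 4: the unpaired test.** For a binary outcome seen before and after in the same n infants, let b be the number positive only after and c the number positive only before. The paired risk difference is (b − c)/n, with large-sample variance [(b + c) − (b − c)²/n]/n². An independent-samples analysis instead uses [p1(1 − p1) + p2(1 − p2)]/n, where p1 and p2 are the proportions before and after. That omits the term −2·Cov/n, where Cov is the within-infant covariance. If an infant's two values are positively correlated, the unpaired analysis overstates the variance. The documents give no rates or correlation, so the amount cannot be calculated.

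**The case against.** The strongest reply is that this is an omission rather than a contradiction. The odds-ratio sentence directly follows the one about the undefined model. The linear regression comes only after two other tests and has its own stated purpose. The sponsor may have meant a logistic model for some categorical outcome and left it out, keeping linear regression for continuous change. That reading is open, and nothing in the text says that the odds ratios come from the linear model. It does not rescue the plan, because the logistic model, its outcome and its confounders are all absent. The plan also applies the word association to the linear regression itself, which invites the odds-ratio sentence to cover it.

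A reader might infer three stronger things, which the documents do not support:

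- That the analyst is forced to dichotomise continuous outcomes. No section proposes this. An odds ratio could be attached to an outcome such as atopic manifestation without cutting anything.
- That the odds ratio would greatly overstate the change. This depends on event rates that the protocol does not give, on which category is coded as the event, and on the odds ratio being read as a risk ratio. It would apply equally if logistic regression had been named, so it has no bearing on the mismatch.
- That the events will be too few for any adjusted model. With 50 infants this is a fair caution, but without an event rate it cannot be quantified.

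It can also be said that the sentence is not tied to the primary outcome and that the remedy is only wording. Both are true, and they limit the weight of the point.

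**Conclusion.** The point holds as a mismatch between measure and analysis: the plan is wrong as written. An odds ratio with a 95% CI is the only effect measure and the only interval it specifies, and none of the five named methods can supply it in adjusted form. The only before/after test for categorical data also disregards the pairing within infants.

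The conclusion rests on reading the whole protocol and on what each method estimates; it needs no assumed rates. It holds whether the odds-ratio sentence was meant for the linear regression or for a logistic model that was left out, since the text needs correcting in either case. It should be put right before analysis. It does not show that any particular result would be biased by a known amount.

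**What to change.** Replace the odds-ratio sentence with text that pairs each type of outcome with an analysis and its own measure:

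1. **Continuous outcomes (SCFAs, abundances, IL-6, IL-10, BMI).** Report associations from the linear regression as adjusted mean differences, or slopes per stated unit, with 95% CIs. Do not dichotomise. List the confounders by name.
2. **Outcomes that are genuinely binary at both times, for example atopic manifestation once defined as present or absent.** Replace the unpaired Mann-Whitney test with an analysis paired within infant, such as McNemar's test, and report the paired risk difference with its 95% CI.
3. **Odds ratios.** Keep them only where the outcome is defined as binary, a logistic model that accounts for repeated measures on the same infant is named, and the event count supports the covariates. If these conditions are not met, delete the sentence.

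The cost is a change of wording in the statistical section. No new data, visits or infants are needed.

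### Categorical before/after comparisons are assigned an unpaired Mann-Whitney test, although both sets of values come from the same 50 infants

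*Combined protocol and SAP*

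**What the plan says.** The analysis text is in Statistical Aspects and Considerations. For categorical data it says: "The Mann-Whitney U test for unpaired samples will be applied to compare different categorical parameter between infants before and after treatment". The sentence just before it, on laboratory data, says: "The non-parametric Wilcoxon test for paired samples will be used to compare different laboratory parameters at different times of collecting samples". The threshold is "A p-value <0.05 will be considered significant"; sidedness is not given.

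The design is described elsewhere. Study Population gives 50 subjects. Conduct of Trial says "All the subjects will be fed organic formula milk as a part of their dietary for 12 weeks", so there is no comparison group. Outcomes gives the aim: "Data will then be calculated to see if there is a significant difference before and after organic formula feeding". Description of Visits says "A visit follow up will be done before and after the study".

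The plan does not list the categorical parameters. It gives no category rates, effect size, power or within-infant correlation, and it names no paired test for categorical data.

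**The concern.** Mann-Whitney compares two independent groups. Here each infant contributes one value to the before set and one to the after set, so the test uses the wrong variance for the difference whenever an infant's two values are correlated. If the correlation is positive, the test is conservative: it creates no false positives but can miss real change. If it is negative, the test rejects too often.

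There is a second problem, which does not depend on correlation. Mann-Whitney ranks the data. For a parameter with three or more categories and no natural order, the p-value depends on which arbitrary number each category is given.

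With no control arm, change within infants is the only before/after contrast the study has. Atopic manifestation, a secondary objective, would be affected if it is recorded as a category; the plan does not say how it is recorded.

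**Working it through.** **Inputs.** From the documents: n = 50 infants, one group, threshold 0.05. Assumed, because the documents are silent: two-sided testing, 50 complete pairs, a binary parameter, the rates shown below, and within-infant correlation phi. The plan has no figure of its own to reproduce.

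**Step 1: size by formula.** For a binary parameter with the same true prevalence p before and after, tie-corrected Mann-Whitney is essentially the pooled two-proportion z test. It assumes Var(difference) = 2p(1−p)/n. With pairing, the true variance is 2p(1−p)(1−phi)/n. The z statistic therefore has standard deviation √(1−phi), and

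size = 2 × [1 − Φ(1.96/√(1−phi))].

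- phi 0: 1.96/1 = 1.96, size 5.0%
- phi 0.2: 1.96/0.894 = 2.19, size 2.8%
- phi 0.3: 1.96/0.837 = 2.34, size 1.9%
- phi 0.5: 1.96/0.707 = 2.77, size 0.6%
- phi −0.2: 1.96/1.095 = 1.79, size 7.4%

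**Step 2: size by exact enumeration** of every paired 2×2 table with n = 50:

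| Prevalence | Test | phi 0 | 0.2 | 0.3 | 0.5 |
|---|---|---|---|---|---|
| 30% | Mann-Whitney | 5.0% | 2.9% | 1.9% | 0.6% |
| 30% | mid-p McNemar | 4.5% | 4.7% | 4.6% | 4.2% |
| 10% | Mann-Whitney | 4.8% | 2.8% | 2.0% | 0.7% |
| 10% | mid-p McNemar | 4.0% | 3.6% | 3.2% | 2.1% |

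The enumeration agrees with the formula.

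**Step 3: power by the same enumeration** (Mann-Whitney / exact McNemar / mid-p McNemar, %):

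| Change | phi 0 | 0.2 | 0.3 | Higher phi |
|---|---|---|---|---|
| 40% to 20% | 60/50/57 | 61/60/68 | 61/66/74 | 63/82/88 (phi 0.5) |
| 5% to 20% | 65/52/62 | 66/61/71 | 67/67/77 | 68/73/84 (phi 0.4) |

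For 5% to 20%, phi cannot exceed 0.46. Against mid-p McNemar, Mann-Whitney is 3 points ahead at phi 0, 5 to 7 points behind at 0.2 and 10 to 13 behind at 0.3. Exact McNemar draws level only at about phi 0.2 in the first row and 0.3 in the second.

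**Step 4: one data set, 20/50 before and 12/50 after.** The difference is 0.16 and the pooled proportion 0.32. The Mann-Whitney variance is 0.32 × 0.68 × (2/50) × (100/99) = 0.00879, so z = 0.16/0.0938 = 1.71 and p = 0.088 (no continuity correction), whatever the pairing. McNemar uses the infants who changed:

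| Changed each way | phi | exact p | mid-p |
|---|---|---|---|
| 13 v 5 | 0.21 | 0.096 | 0.064 |
| 12 v 4 | 0.31 | 0.077 | 0.049 |
| 11 v 3 | 0.40 | 0.057 | 0.035 |
| 10 v 2 | 0.50 | 0.039 | 0.022 |

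For 12 v 4, exact p = 2 × P(X ≤ 4), X binomial(16, ½), = 2 × 2517/65536 = 0.077. The mid-p value subtracts P(X = 4) = 1820/65536 = 0.028, which gives 0.049. The verdict at 0.05 changes from phi about 0.3 with mid-p, and about 0.5 with exact McNemar.

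**Step 5: unordered categories.** Take three categories with counts 20/20/10 before and 10/30/10 after. Of the six possible numeric codings, four give Mann-Whitney p = 0.13 and two give p = 0.024. The data are identical each time.

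**The case against.** The strongest objection is that a paired test need not gain power. These are healthy infants, so some categories may be rare. For an assumed rise from 2% to 10%, power (Mann-Whitney / exact / mid-p McNemar) is 38/20/32% at phi 0, 37/21/34% at 0.2 and 35/21/35% at 0.3. At 5% prevalence the mid-p test is itself the more conservative: its size is 2.3%, 1.5% and 1.1% at phi 0, 0.2 and 0.3, against 4.3%, 2.5% and 1.7% for Mann-Whitney. This stands: the power effect depends on prevalence as well as correlation, and can go either way. It does not make a test of independent groups valid for paired data.

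It is also fair to say that mid-p is one choice among several McNemar versions, that the worked verdict depends on that choice, and that no named endpoint is shown to be affected. The unordered example corresponds to no variable the documents identify. These points limit the practical consequence but leave the defect in place.

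A more charitable reading is that the sentence means a comparison between different groups of infants. The plan defines no such groups, and the contrast it states is before against after treatment.

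**Conclusion.** The concern holds. The plan names an unpaired test for data that its own design makes paired, next to a sentence that handles the same design correctly for laboratory values. That conclusion rests on the text alone and needs no assumed figure.

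The size of the effect does rest on assumptions. With positive correlation and categories that are not rare, the cost is lost power: nothing at phi 0, modest at 0.2, and 25 points against mid-p McNemar at phi 0.5 for 40% to 20% (88 − 63). For rare categories a paired test may gain nothing or lose a few points. With negative correlation the planned test rejects too often.

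The reach is limited to the unnamed categorical comparisons, and no effect on the primary tolerance result is claimed. This should be fixed, but it does not threaten the study as a whole.

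**What to change.** Replace the Mann-Whitney sentence with text such as:

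*For each infant, binary parameters before and after treatment will be compared with McNemar's test (mid-p), ordered categories with the Wilcoxon signed-rank test, and unordered categories with the Stuart-Maxwell test of marginal homogeneity.*

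Three additions complete it:

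- List the categorical parameters covered, and say whether atopic manifestation is one of them.
- Say which visit counts as after. Outcomes states "We will measure the outcome every month" for tolerance, so more than one follow-up value may exist.
- Keep Mann-Whitney only for comparisons between different infants, and name those groups if any are intended.

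Exact McNemar is also valid, with less power at this sample size; whichever version is used should be fixed before the data are analysed. The cost is a change of wording in the analysis section. It needs no new data or visits, because each infant is already measured before and after.

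### No analysis of new atopic cases is specified, and the one before/after test named for categorical parameters reflects net change, which could mask them

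*Combined protocol and SAP*

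**What the plan says.** Objectives of Trial lists "Atopic manifestation" as a secondary objective, and Outcomes names it again among the measurements. Neither gives a case definition or scale.

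Allergy information is collected repeatedly. Conduct of Trial states: "Every month the parent will be called in order to assess for child's sickness, allergy". Description of Visits, which covers the assessments before and after the feeding period, adds: "We will also collect the allergy related data".

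Entry is open to "Healthy infants 6-7 months of age". The inclusion and exclusion lists cover congenital, thyroid, gastrointestinal, severe and nutritional conditions. They do not mention existing atopy.

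Statistical Aspects and Considerations does not name atopic manifestation. For categorical data it names an unpaired Mann-Whitney U, to "compare different categorical parameter between infants before and after treatment". It also mentions a confounder-adjusted model reported as odds ratios and linear regressions of change, without naming the outcomes of either. The threshold is "A p-value <0.05 will be considered significant". No analysis of new cases, resolved cases or first occurrence is described.

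**The concern.** If atopic manifestation is handled by the one categorical before/after test on offer, the result describes how the prevalence moved, not how many unaffected infants became affected. Two things can make these differ:

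- **Resolution.** An infant affected at entry who recovers offsets an infant who becomes affected.
- **Clearing between visits.** Signs that appear after the first visit and are gone by the last leave no trace in a two-point comparison, although a monthly contact may have recorded them.

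The product is labelled as containing milk and soy, and the primary outcome is tolerance. A non-significant net change could then be read as reassurance about allergy when the data needed to answer the question directly had been collected and not used.

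**Working it through.** **Inputs.** From the documents: 50 infants in one group, 12 weeks of feeding, threshold 0.05 (two-sided assumed). Not in the documents: baseline frequency of atopy, frequency of new onset, frequency of resolution, dropout. All counts below are assumptions, with no dropout. The plan has no figure of its own on this point to reproduce.

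**Formulas.** Let n = 50, with a infants affected before and c affected after, so c = a + new − resolved.

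- Unpaired Mann-Whitney U on a yes/no variable (normal approximation, ties corrected, no continuity correction): z = [(c − a)/n] / √[2p(1 − p)/n] × √[(2n − 1)/(2n)], with p = (a + c)/(2n). Only a and c enter, so equal numbers of new and resolved cases give z = 0 whatever the number of new cases.
- Exact McNemar: two-sided binomial test of the new cases out of (new + resolved) against 0.5. For 6 v 0 this is 2 × 0.5⁶ = 0.031.
- New onset: new/(50 − a), with a Clopper-Pearson 95% CI.

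**Results.**

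| Affected at entry | New | Lost by the last visit | Status before → after | Mann-Whitney p | McNemar p | New onset (95% CI) |
|---|---|---|---|---|---|---|
| 0/50 | 6 | 0 | 0 → 6 | 0.012 | 0.031 | 6/50 = 12.0% (4.5% to 24.3%) |
| 0/50 | 6 | 4 of the 6 new cases clear | 0 → 2 | 0.16 | 0.50 | 6/50 = 12.0% (4.5% to 24.3%) |
| 5/50 | 5 | 5 resolve | 5 → 5 | 1.00 | 1.00 | 5/45 = 11.1% (3.7% to 24.1%) |
| 10/50 | 5 | 5 resolve | 10 → 10 | 1.00 | 1.00 | 5/40 = 12.5% (4.2% to 26.8%) |
| 10/50 | 8 | 4 resolve | 10 → 14 | 0.35 | 0.39 | 8/40 = 20.0% (9.1% to 35.6%) |

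In row 2 the two-point table shows only 2 new cases, so McNemar is 2 v 0: 2 × 0.5² = 0.50.

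**Chance of detecting an increase.** Simulated with 1,500 runs per scenario and new onset of 15% in unaffected infants:

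| Baseline prevalence | Resolution | Mann-Whitney | Exact McNemar |
|---|---|---|---|
| 0% | not applicable | about 95% | about 78% |
| 10% | 0% / 30% / 60% | 40% / 25% / 15% | 67% / 32% / 13% |
| 20% | 0% / 30% / 60% | 13% / 4% / 1% | 57% / 9% / 1% |

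Replacing the unpaired test with a paired one helps when little resolves. It does not by itself deal with resolution.

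**The case against.** The strongest reply is that the statistical section assigns no test to atopic manifestation at all. A reader might infer that this outcome is compared only as a before/after category. The documents do not say so: the categorical parameters are unnamed, and the odds-ratio model could have atopy as its outcome. This stands. What remains is narrower: no analysis of new cases is written down, and the one categorical before/after test that is named would not supply it.

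A reader might also infer that new cases will be cancelled. That is conditional. Healthy infants are recruited, no baseline rate is given, and without cases at entry the two-point comparison loses only signs that clear before the last visit. However, nothing defines healthy so as to exclude existing atopy.

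It would also be too strong to say that a paired test sees only the difference between new and resolved cases. McNemar uses both counts: a net gain of 4 gives p = 0.125 for 4 v 0 but 0.39 for 8 v 4. The paired 2×2 table also shows new and resolved cases separately. Only the unpaired test depends on prevalence alone, and using it on the same infants before and after is a defect in its own right.

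Finally, calling this a lost safety signal goes beyond the documents. Atopic manifestation is a bare secondary objective, and the Introduction presents microbiota as possibly preventing allergic disease, so improvement in affected infants may interest the investigators equally. That is a reason to report onset and resolution separately.

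**Conclusion.** The point holds in a limited form. A stated secondary objective has no analysis of new cases, and the only before/after test named for categorical parameters reflects net change in prevalence. Masking requires either infants who enter with atopy that then resolves, or signs that come and go between the first and last visits. The entry criteria exclude neither.

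The size depends wholly on assumed rates. It runs from no loss (no cases at entry, none clearing) to complete loss (equal numbers new and resolved, p = 1.00 with new onset of 12.5%). The documents do not show where in that range this trial would fall. Nor do they support a claim that a safety finding will be missed. This is an inexpensive improvement to a secondary outcome, not a flaw that undermines the study.

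**What to change.** In the protocol, give one case definition of atopic manifestation and apply it in the same way at baseline, at each monthly contact and at the end. In the statistical section:

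1. Report first occurrence at any contact up to week 12, among infants free of atopic manifestation at baseline, as a proportion with an exact 95% CI.
2. Report resolution or persistence separately for infants affected at baseline.
3. Show the paired before/after 2×2 table as description, with McNemar in place of Mann-Whitney.

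**Cost.** A case definition and a few sentences in the statistical section; the allergy data are already planned. The denominator falls somewhat below 50 if any infant is affected at entry. The monthly information may rest on parent report, because the protocol does not make clear whether that contact includes an examination; if ascertainment differs from baseline, apparent new onset could be distorted. With no control group, new cases over 12 weeks cannot be attributed to the formula, and the report should say so.
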